Kintsugi, a digital health technology company based in Berkeley was founded to address these challenges. Kintsugi initially started by creating a consumer application, a voice journaling wellness app that is available on the Apple App Store. This app allows users to journal by speaking, interact with community members who share similar challenges, and track their wellness and mental health over time to promote mental wellbeing. Based upon their preliminary work and user engagement, the Kintsugi team applied for and was awarded several National Science Foundation Small Business Innovation Research (SBIR) grants to develop new Artificial Intelligence (AI) technologies in healthcare. Most recently, the team is developing an AI-based algorithm that is able to detect signs of depression and anxiety from short clips of free-form speech. The Kintsugi Voice Device is the result of these efforts.

Voice biomarker technologies provide a unique way to scale access to mental healthcare by assisting clinicians with the screening and triage especially in high-volume environments where administrative burdens are high and mental health conditions are often overlooked. Researchers have attempted to find objective methods to increase the accuracy of depression and generalized anxiety disorder diagnoses, and voice-based biomarkers are attractive because of their non-invasive nature and ability to provide passive monitoring.

Study Device Description

The Kintsugi Voice Device (“Device”) is a software API that allows the clinician to upload a voice sample for analysis from an individual ≥ 22 years old. The API can be electronically interfaced and perform analysis with data transferred from computer-based applications. The Kintsugi Voice Device output is adjunct to clinical assessment and provides a sensitive reliable estimate of the presence of vocal characteristics consistent with a significant depressive episode and/or a clinically significant anxiety state, which are a necessary condition for the diagnosis of lifetime mood disorders, such as major depressive disorder and/or generalized anxiety disorder. The Kintsugi Voice Device is not to be used in-lieu of full patient evaluation or relied upon to make or confirm diagnosis but offers objective signals in the global assessment of mood and anxiety disorders.

The Device comprises of the following:

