Once processed, vocal features are extracted from the audio and inputted into the neural network models. The software interprets the acquired signals using signal processing and an artificial neural network to quantitatively evaluate voice characteristics for presence of indicators correlated to depression and anxiety. The Kintsugi Voice Device then generates an output for signs of depression and anxiety which is displayed to the Device Operator. The Kintsugi Voice Device output will be positive for depression or negative for depression and positive for anxiety or negative for anxiety. The outcome can also be “uncertain” or within an “indeterminate range” if the Device cannot provide a high-confidence result.

Study Objectives

This study seeks to evaluate the ability of the Device to aid clinical assessment for depression and anxiety by comparing its output with the established diagnostic standard consisting of a diagnosis made by a specialist clinician based on DSM-5 criteria.

This is a prospective study of up to 100 subjects, ages ≥ 22 years of age.

We are striving for a 50%/50% split of subjects who have depression and/or anxiety and subjects who do not have depression and/or anxiety.

Study Endpoints

Effectiveness Endpoints

The primary endpoints of this study are to:

1. Determine the specificity and sensitivity of the Device in discriminating the presence of a significant depressive episode using the Structured Clinical Interview for DSM-5 Clinical Trial Version as the established diagnostic standard (“gold standard”)
2. Determine the specificity and sensitivity of the Device in discriminating the presence of a clinically significant anxiety state using the SCID-5-CT as the established diagnostic standard

The secondary endpoints of this study are:

- Measurement of the percentage of all adults for whom the Device provided no result
- Determine the specificity and sensitivity of the Device in discriminating the presence of a significant depressive episode compared to the PHQ-9
- Determine the specificity and sensitivity of the Device in discriminating the presence of a clinically significant anxiety state compared to the GAD-7

Safety Endpoints

Adverse events (AEs) and serious adverse events (SAEs) will be collected and reported from enrollment, which is determined by informed consent signature, through the completion of the study.

Study Duration

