The study is expected to last up to 8 months. The duration of each individual subject’s involvement in the study will be approximately 2 hours total consisting of a screening call followed by a psychiatrist clinical evaluation and online survey. However, participants could be active on the study for up to 2 weeks to schedule a SCID assessment.

Study Design and Procedures

This is a prospective fully remote, decentralized clinical study to measure the sensitivity and specificity of the Device predictions against clinical ground truth for major depressive disorder and for generalized anxiety disorder. Up to 100 participants will undergo investigational and comparator assessments for major depressive disorder and a clinically significant anxiety state.

The research coordinator will schedule a time with the participant for the evaluation. There will be a two-part evaluation: a web-based study survey and a specialist clinician evaluation via the SCID assessment. The SCID assessment will include questions about the past medical history of the participant as well as questions from the Clinical Global Impression - Severity scale. The order of the two evaluations will be randomized to minimize any potential bias.

The Device output will be positive for depression, negative for depression, or indeterminate for depression and positive for anxiety, negative for anxiety, or indeterminate for anxiety. PHQ-9 and GAD-7 scores will also be collected through the Study Survey.

Participants will also be evaluated by a specialist clinician via the SCID assessment. The psychiatrist performing the SCID assessment will be a board-certified psychiatrist. The clinical evaluation via the SCID assessment will be recorded and the channel-separated audio file of the participant during this assessment will be used as the Device input. The input for the Device will be obtained by the clinical research team and will be at least one minute of audio taken from the SCID assessment where the participant is asked about their current illness history and treatment history. The results of these assessments will act as the clinical comparator for comparison with the Device output.

Clinicians and participants will both be blinded to the participant the Device output and the participant assessment results (SCID, PHQ-9, GAD-7). Further, a SCID reviewer may review the recorded SCID assessment and standard clinical assessment and completed SCID template to minimize interrater variability.

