The SCID assessment will be conducted by a specialist. Specialists will have board certification in psychiatry and have at least two years of experience diagnosing depressive and anxiety disorders. Specialists will also undergo psychiatric assessment scoring training for the SCID assessment prior to providing diagnoses for the study to minimize discrepancies in scoring.

Participants will complete the SCID assessment through a HIPAA compliant teleconferencing application such as Zoom Meetings. The meeting will be recorded, and the participant will need to consent to the recording in order to participate in the study. After the SCID assessment, the specialists will determine a diagnosis based on whether the participant meets the DSM-5 criteria for Major Depressive Disorder and Generalized Anxiety Disorder.

Once the Study Survey (voice sample, PHQ-9, GAD-7) and the specialist-evaluated SCID are complete, the participant will receive an Amazon gift card of \$50 for their time.

Study Population

This study will enroll up to 100 subjects ≥ 22 years old. Only subjects who meet all eligibility criteria and sign the informed consent will be enrolled.

Inclusion Criteria

- Subjects ≥ 22 years of age at the time of informed consent
- Participant must be able to read, understand and sign the Informed Consent Form
- Access to a laptop, smartphone, tablet, or other Device with a functioning microphone
- Participants must be willing to be videotaped as part of the study
- Stated willingness to comply with all study procedures and availability for the duration of the study
- Fluency in English
- Availability for the duration of the study
- The participant must reside within the state of California

Exclusion Criteria

Participants with at least one of the following conditions will be excluded:

- Any impairment that would prevent participants from completing an online survey and/or engage in clinician assessment interviews (e.g., visual impairment, motor impairment, hearing impairment, acute intoxication)
- Any known history of neurodegenerative or Central Nervous System disorders
- Any known history of schizophrenia, psychosis, or severe cognitive deficits
- Any known presence of disorders that may lead to false signal of depression or anxiety including Multiple Sclerosis, Amyotrophic Lateral Sclerosis, Parkinson's Disease, Stroke, Traumatic Brain Injury

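### Device speech is cut from the illness-history part of the SCID that also gives the reference diagnosis, so accuracy may reflect topic as well as disease, and randomising the survey order cannot separate the two

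*Protocol*

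**What the plan says.** - **Index test.** Under Study Design and Procedures, the "channel-separated audio file of the participant during this assessment will be used as the Device input". The excerpt is "at least one minute of audio taken from the SCID assessment where the participant is asked about their current illness history and treatment history". On who takes it: "The input for the Device will be obtained by the clinical research team". The same section states blinding for clinicians and participants only.
- **Reference.** Study Endpoints defines both primary endpoints against the SCID, the depression endpoint "using the Structured Clinical Interview for DSM-5 Clinical Trial Version as the established diagnostic standard". The procedures under Randomization add: "After the SCID assessment, the specialists will determine a diagnosis based on whether the participant meets the DSM-5 criteria".
- **Bias control.** "The order of the two evaluations will be randomized to minimize any potential bias". The two evaluations are the web survey and the SCID.
- **Fallback.** Under Randomization, if the SCID audio cannot be scored, for instance because it is too short, the participant may be asked for another sample. No prompt or setting is given for it.
- **Where the sample is taken.** A later paragraph of the same procedures places it in the survey: "Once the Study Survey (voice sample, PHQ-9, GAD-7) and the specialist-evaluated SCID are complete". Subject Compensation (Financial Considerations) lists only the PHQ-9 and GAD-7 there.
- **Speech the algorithm is meant for.** Background Information says it is developed to "detect signs of depression and anxiety from short clips of free-form speech".

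**The concern.** The chosen topic is one on which cases and non-cases naturally have different things to say. A participant with depression or anxiety can narrate symptoms and care, while a participant without illness may have little to report. Pauses, speech rate and hesitation can change with that difference, apart from any effect of the disorder on the voice.

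Index sample and reference diagnosis also come from one session. A reader could take the randomised order as protection for the Device-versus-SCID comparison, but it does not separate those two.

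At stake is what the two primary results mean: whether the estimates describe detection of disease from speech, or detection of disease from speech about being ill. A later analysis plan could not repair this if no other speech had been recorded.

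**Working it through.** The Protocol gives an upper limit of 100 participants and an aimed 50/50 split, but no target sensitivity or specificity. There is no figure to reproduce, so the check is mainly of the text.

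**1. Position of the Device sample under each order** (sample taken as in Study Design and Procedures)

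| Order drawn | First | Second | Device sample | Reference diagnosis |
|---|---|---|---|---|
| A | Survey | SCID | inside SCID | from SCID |
| B | SCID | Survey | inside SCID | from SCID |

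The last two columns are identical. The randomisation can balance any effect of answering the questionnaires first on interview answers and speech. It cannot separate the Device sample from the reference interview. It would do so only if the sample were in the survey, as the one paragraph under Randomization has it.

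**2. Can topic reach an acoustic device?** Principles of Operation names speech rate, hesitation and pause time among the reported markers of depression. System or Device Components Description lists trimming of pauses only at the two ends of the file, so pauses within the excerpt are not listed for removal. Manner of speech that varies with topic can therefore reach the model. That it differs by case status is an inference from the prompt, not a statement in the Protocol.

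**3. Fallback.** The Device needs at least 60 seconds of voice (Study Device Description). A participant with little illness to describe is more likely to fall short and be asked for another sample. Since that prompt is not fixed, the source of the speech may itself differ by case status.

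**4. Scale, on assumed values only.** Let Se be sensitivity on topic-neutral speech and d the shift that topic adds to the Device score in cases, in SD units, with one threshold and indeterminate results ignored:

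apparent sensitivity = Φ(z(Se) + d)

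With Se = 0.70, z = 0.524:

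| d | Apparent sensitivity |
|---|---|
| −0.3 | Φ(0.224) = 0.589 |
| 0.1 | Φ(0.624) = 0.734 |
| 0.2 | Φ(0.724) = 0.766 |
| 0.3 | Φ(0.824) = 0.795 |
| 0.5 | Φ(1.024) = 0.847 |

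Starting from Se = 0.60, d = 0.3 gives 0.710; from 0.80 it gives 0.873.

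Sampling error for comparison, as a 95% half-width = 1.96 × √(Se(1 − Se)/n):
- n = 50: 1.96 × √(0.70 × 0.30/50) = 0.127.
- n = 40, if 20% of 50 are indeterminate (the Protocol's glossary expects up to 20%): 0.142.

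A shift of 0.3 SD moves the estimate by 0.795 − 0.700 = 0.095, about three quarters of the half-width at n = 50. A shift of 0.5 SD moves it by 0.147, more than either half-width. Fifty cases for one endpoint is itself generous. The 50/50 aim concerns depression and/or anxiety against neither, so 50 cases per endpoint at 100 participants would require every case to have both conditions.

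**The case against.** The strongest reply has five parts.

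- **Direction.** A reader might infer that accuracy is inflated. The Protocol does not support that as a conclusion. Short answers with long pauses could sound depressed under its own list of markers, which would lower specificity. Depression and anxiety are separate endpoints, so an anxiety case without depression is a non-case for depression yet still has distress to describe. Recruitment may draw on people interested in mental health, so non-cases may have a history to tell. This stands: optimism is plausible, not shown.
- **Size.** A reader might equate the share of topic-driven calls with points of inflation. A call driven by topic raises accuracy only if it would otherwise have been wrong. At an assumed sensitivity of 0.70, even wholly helpful topic effects on 5% to 15% of calls add 0.30 × 5 = 1.5 to 0.30 × 15 = 4.5 points. This stands too.
- **Incorporation bias.** The term is tempting, but clinicians do not see the Device output, the participant's audio channel is separated, and the diagnosis follows a structured interview by trained specialists. The Device result does not enter the diagnosis. What remains is shared, status-dependent elicitation.
- **Order randomisation.** The Protocol states only a general aim of reducing bias and never claims to separate index test from reference. Balancing questionnaire priming is a real benefit, so it would be wrong to call the step useless.
- **Intended use.** The Device is meant for clinical workflows, where talk about illness is realistic, and the 60-second minimum limits very short inputs. This is fair, but the Device description does not restrict use to illness-history answers given to a psychiatrist, and the minimum sends short talkers to an unspecified prompt.

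**Conclusion.** The point holds in a limited form. By the text, the Device sample and the reference diagnosis come from one interview, the sample is taken from a topic tied to illness, and the randomised order does not separate them. By sound inference, the elicited speech, and through the fallback its source, may differ by case status. Both primary endpoints are exposed.

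Sensitivity and specificity may therefore reflect topic as well as disease and may not carry over to free-form speech in general. Neither size nor direction can be derived from the Protocol. The values above show only that, on assumed inputs, a moderate shift could be comparable to the sampling error.

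Two further matters add to this. The staff who obtain the excerpt are not stated to be blind to the SCID result. The Protocol also contradicts itself on whether the voice sample belongs to the survey or the SCID. The design should be changed while the missing speech can still be collected.

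**What to change.** 1. Reconcile Study Design and Procedures, the procedures under Randomization, and Subject Compensation on where the voice sample is taken.
2. For every participant, record at least 60 seconds on one fixed illness-neutral prompt in the Study Survey, before the PHQ-9 and GAD-7. The paragraph that lists a voice sample in the survey already allows this, and the randomised order would then apply to that sample. Use the same prompt for any replacement sample.
3. Run the Device on both the neutral sample and the SCID excerpt, report sensitivity and specificity for both, and name in advance which is primary.
4. Have the SCID excerpt chosen by a fixed rule, by staff blind to the SCID result.
5. If no new recording is made, run the Device on a fixed non-symptom part of the SCID recording as a sensitivity analysis, and limit the accuracy claim to illness-history interview speech. This removes the topic effect but not the shared session.

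Cost: a protocol amendment and about one extra minute per participant; the fallback in step 5 needs no new recording. Measured accuracy may turn out lower.

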Subject Identification and Recruitment, Process of Consent

Subjects may be recruited through various mediums including but not limited to social media, Craigslist, and/or specialized clinical trial recruitment groups. At the time of enrollment, the mental status of the participant will not be known. Subjects may be recruited from populations that self-select as interested in mental health. Potential subjects will be provided with detailed study information so that they are able to make an informed decision.

If subjects wish to enroll, they will need to answer brief pre-screening questions about the inclusion/exclusion criteria to determine if they meet the study inclusion/exclusion criteria. Subjects ineligible for the study will be told they do not qualify. Subjects eligible for the study will receive an informed consent form if they are interested in participating. Participant identity will be verified before enrollment.

Participants will then schedule a time for the SCID assessment and to take the web-based study survey within the same day. Study participants can choose to end participation in the study at any time. The clinical research coordinator will also answer any questions on the study that participants have prior to enrollment.

Participants will also provide basic information such as their physical address, emergency contact, age, and email. Only the necessary participant information and medical history required for the study will be collected.

Recruitment will continue until up to 100 participants have SCID results or until the Sponsor terminates the study. The Sponsor may collate interim results at any time during the study to determine whether the study should continue.

[figure not shown]
Process of Consent

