The participant will be given access to the informed consent form. The informed consent form serves to ensure that participants understand the purpose of the study, assessments the participants will be asked to undertake as part of the study, the risks and benefits of participating, and the voluntary nature of their participation. The informed consent form will inform the participants that they will provide a recording of their voice and video as part of the study. The informed consent form will also inform the participants that their specialist SCID assessments conducted over a HIPAA-compliant video-conferencing platform will be recorded for the purposes of the study and research. A copy of the consent form will be provided to the participant after they consent. A clinical research coordinator will be available to answer participant questions about the study.

Randomization

The order in which the online survey and SCID assessment occur will be randomized. All participants will participate in investigational (Kintsugi Voice Device) and comparator assessments (SCID assessment, PHQ-9, and GAD-7).

Figure 2: Study Design Flow

A schematic of the study steps is illustrated in Figure 2.

Participants will be considered enrolled once they have signed the informed consent form.

Participants will receive instructions on completing our web-based Study Survey. If the audio sample from the SCID assessment is not scorable (e.g. poor microphone quality, insufficient length, excessive background noise), the participant may be asked to submit an additional audio sample. A clinical research team member will run the audio sample through the Device. Participants will fill out the PHQ-9 and GAD-7 questionnaires as part of the Study Survey. The Device output, PHQ-9, and GAD-7 results will not be shared with the clinicians. Similarly, the Device output, the PHQ-9, and GAD-7 results will not be shared with the participants.

Participants will complete a SCID assessment immediately after or immediately before the web-based Study Survey. A clinical research coordinator will be available to support the participant if they run into issues with the Study Survey.

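### PHQ-9 and GAD-7 results are withheld from clinicians with no safety exception, so a severe answer given after the SCID, or by someone who leaves before it, has no stated route to a clinician who can act

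*Protocol*

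**What the plan says.** **Blinding.** Study Design and Procedures has one sentence on it: "Clinicians and participants will both be blinded to the participant the Device output and the participant assessment results (SCID, PHQ-9, GAD-7". The text after Figure 2, under Randomization, gives the rule again in two parts. For clinicians: "The Device output, PHQ-9, and GAD-7 results will not be shared with the clinicians". For participants: "Similarly, the Device output, the PHQ-9, and GAD-7 results will not be shared with the participants". None of these sentences has an exception or an end date.

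**Order and withdrawal.** The order of survey and interview is randomized: "Participants will complete a SCID assessment immediately after or immediately before the web-based Study Survey". Subject Identification and Recruitment adds: "Study participants can choose to end participation in the study at any time". Participant Withdrawal Criteria keeps the data of anyone who leaves early and uses them in the research.

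**Emergency provision.** Potential Risks describes an emergency contact, a possible 911 call and referral to local resources. These depend on the psychiatrist or clinician judging that there is imminent danger or an emergency.

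**Diagnosis and benefit.** After the SCID, "the specialists will determine a diagnosis based on whether the participant meets the DSM-5 criteria" for the two disorders. Potential Benefit says that taking part might identify depression or anxiety and so bring treatment forward. Of the state of participants on entry, the protocol says: "At the time of enrollment, the mental status of the participant will not be known".

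**The concern.** The survey measures the severity of depression and anxiety in a fully remote study that aims for about half of its participants to have one or both conditions. Some answers may be severe. The person named to act in an emergency is the psychiatrist, who is barred from seeing those answers. If the interview is already over, or never takes place, the rule as written leaves a severe answer with no one assigned to look at it.

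At stake are participant safety and the coherence of the protocol's own safety provision. Sensitivity, specificity, error rates and sample size are not affected.

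**Working it through.** No arithmetic applies, because the protocol states no figure on this point and the point needs none. The check is to follow a severe survey answer along each path and look for a stated route to someone who can act.

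**Step 1: the paths.**
- *Survey, then SCID.* The psychiatrist does not see the answers but interviews the participant straight afterwards. Danger can come to light in that interview, and the emergency provision can be used.
- *SCID, then survey.* The planned clinician contact has ended when the survey is answered. The answers are withheld from the psychiatrist, and no later contact is planned.
- *Survey, then withdrawal before the SCID.* No clinician contact takes place. The answers are kept and used for research.

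On the second and third paths, the emergency provision cannot be triggered by what the survey shows.

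**Step 2: other parts of the protocol that might fill the gap.**
- The coordinator is available during the survey, but to help with problems in completing it. No safety review of answers is assigned.
- Data Collection and Storage lets several groups view study information. It gives permission, with no duty to look and no time limit.
- Recording of AEs/ADEs and SAEs/SADEs covers events that staff observe or participants volunteer, and two study clinicians review them. Questionnaire answers are not mentioned.
- The definition of Principal Investigator includes responsibility for participants' safety and welfare. This is a general duty and does not say that anyone reads the survey in time.

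None of these is an escalation route.

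**Step 3: whether the gap is needed to protect the endpoints.** Rater blinding is sound in a diagnostic accuracy study: the SCID is the reference standard, and the Device and questionnaires are compared with it. That requires the blind to hold for whoever rates or reviews a SCID, until that rating is final. It does not require that no clinician ever sees a severe answer.

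**Step 4: the SCID in the blinding list.** Three statements do not fit together:
- Study Design and Procedures lists the SCID among the results withheld from both clinicians and participants.
- The list for participants under Randomization names the Device output, PHQ-9 and GAD-7, and omits the SCID.
- The specialists themselves make the SCID diagnosis, so they cannot be blinded to it.

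The sentence in Study Design and Procedures is visibly garbled. The likeliest explanation is a drafting error, and the protocol leaves open whether participants may learn their SCID result.

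**The case against.** **Existing cover is substantial.** A board-certified psychiatrist interviews every completer on the same day, immediately before or after the survey, with the emergency measures to hand. A participant who takes the survey last would have to disclose online a danger that was not apparent shortly before. The withdrawal path requires leaving between two adjacent steps, and those who withdraw are not paid. This stands, and it makes the gap narrow. It does not close it.

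**The word clinicians may mean only the SCID raters.** Nothing expressly bars the investigator or the research team from seeing survey answers. This also stands in part: what is missing is a stated procedure. But the psychiatrist is the one whose judgement triggers the emergency provision, and no one else is told to look.

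**The protocol gives no item content and no risk threshold.** It describes the PHQ-9 and GAD-7 only as severity scales. That is why the threshold should be set by the sponsor and IRB.

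**The consent form and Figure 2 are not available.** Potential Risks refers to the consent form for emergency handling, so it may say more. Nothing is claimed about either. A separate procedure that sent answers to the SCID clinicians would still conflict with the unconditional rule in the protocol.

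**Stronger readings that the text does not support.** A reader might infer that the blinding rule defeats the stated benefit of identification and earlier therapy. That would take the SCID entry in a garbled sentence as a firm rule for participants while treating the same entry as a slip for clinicians. The omission of the SCID from the participants' list under Randomization points the other way, and the benefit is stated only as a possibility. A reader might also infer that everyone randomized to take the survey last is at risk. Being on that path is not a measure of risk.

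**Conclusion.** The point holds in a limited form. As written, the protocol withholds survey results from the clinicians without exception and ties emergency action to the psychiatrist's own judgement. A severe answer given after the interview, or by someone who leaves before it, therefore has no stated route to a clinician who can act.

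The weight is minor to moderate. No number of affected participants can be given, because the protocol states no ratio for the two orders, no drop-out rate and no rate of severe answers. The change is worth making because it is cheap and leaves the blind intact.

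The conclusion assumes that the clinicians in the blinding rule include at least the psychiatrists who conduct the SCID, and that no unseen document sets an escalation procedure. The SCID entry in the blinding list is a wording matter only.

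**What to change.** **Safety exception.** Add it to both blinding statements, in Study Design and Procedures and under Randomization. The sponsor and IRB set a high-risk threshold for survey answers in advance. Answers above it go the same day to one of:
- an existing study clinician who neither rates nor reviews SCIDs. The clinicians who review adverse events are candidates if the protocol states that they do not rate or review;
- the rating psychiatrist, but only after that participant's SCID rating is locked. Where no SCID has been done, only the non-rating clinician receives them.

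The recipient has authority to use the emergency provision under Potential Risks. The blind to Device output, PHQ-9 and GAD-7 otherwise stays.

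**Wording correction.** Remove the SCID from the clinicians' blinding list and align the two statements. State whether participants may learn the SCID result once the assessments are final, so that the rule agrees with Potential Benefit. Final should include any SCID review and confirmation that the audio is scorable, since otherwise "the participant may be asked to submit an additional audio sample" after the diagnosis is known.

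**Cost.** A short amendment with IRB approval, a little clinician time, and a small risk that answers leak to a rater, which is contained by keeping the recipient apart from rating and review. In a rare emergency before the interview, that SCID may be delayed or lost.
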